Aim 1. To determine the effect of Allopurinol treatment on GFR of hyperuricemic pediatric CKD patients. In a randomized controlled study, pediatric CKD patients with hyperuricemia (serum UA ≥ 5.5 mg/dL) will be allocated 2:1 to Allopurinol versus standard of care (SOC) control for 6 months. Participants will be stratified into two cohorts by disease etiology (cohort A: non-glomerular, cohort B: glomerular). Equal allocation of race is expected as our local population is composed of 50% black race. The primary outcome measure is the amount of GFR change from baseline to 6 months compared to the control group in both cohorts. Secondary outcomes are measurement of the amount of UA and BP change from baseline to 6 months.

Aim 2. Establish whether Allopurinol treatment reduces Nlrp3 inflammasome and renal injury biomarkers. In this exploratory aim, urine and serum biomarkers of Nlrp3 inflammasome activation (hs-CRP, XO enzyme activity, Nlrp3, IL-1 β , IL-18) and renal injury (KIM-1, ET-1, NAG, and NGAL) will be collected at 3 and 6 months and compared to baseline of cohorts A and B treatment and control groups.

Impact: GFR change from baseline to 6 months by treatment and cohort will be used to directly inform the effect size and sample size calculations required for a randomized controlled multicenter pediatric intervention trial. The simultaneous and novel exploration of the effect of XO inhibition on inflammation and renal injury biomarkers will provide crucial data that may identify mechanism of the XO inhibition effect.

BACKGROUND AND SIGNIFICANCE

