1.1. Rationale and Objective: While there is support in the literature for beneficial effect of XO inhibitor therapy on GFR and BP in pediatric CKD, the degree of expected change in GFR based on disease etiology is uncertain. Therefore, we propose a randomized controlled trial of hyperuricemic pediatric CKD participants in a 2:1 allocation between Allopurinol and standard of care (SOC) therapy, and stratified by disease etiology (cohort A: non-glomerular, cohort B: glomerular). Randomization procedure will be blinded, but the allocation will be unblinded to investigator and participant because of the lack of placebo. Allopurinol will be titrated to reach a normal range of serum UA 3-5 mg/dL by 6 months. Local SOC practice for pediatric CKD includes control of blood pressure with anti-hypertensives, control of acidosis, control of proteinuria, and frequent laboratory monitoring to measure the rate of renal function decline. The primary outcome of Aim 1A is change in GFR between baseline and 6 months by treatment group. The secondary outcomes are change in serum UA, and change in BP over the same time. An exploratory sub-aim (Aim 1B) will identify and compare GFR change by cohort characteristics (disease etiology, proteinuria, and race) that may influence future trial designs.

1.2. Experimental Design (Table 1): We will conduct a 6-month randomized treatment (Allopurinol) vs. SOC clinical trial to measure change in GFR over time in pediatric hyperuricemic CKD participants. We will conduct this study after obtaining appropriate consent and assent. Our recruitment pool will include all patients receiving medical care from the CHoR Pediatric Nephrology Division, new and recurring outpatient encounters. The division currently sees approximately 3,500 outpatient encounters per year. The study visits will coincide with SOC visits with the possible exception of visit V1A (some but not all participants will normally be seen for SOC 1 month after the baseline visit). The following inclusion and exclusion criteria apply:

- Inclusion Criteria: CKD stage 1-5; Age 2-20 years old at time of enrollment; Hyperuricemic
- Exclusion Criteria: Contraindication to Allopurinol; Elevated baseline liver function tests; Receiving acute or chronic dialysis; Primary metabolic disorder; Sickle cell disease; Autosomal Dominant Polycystic Kidney Disease; Cystinosis; Bartter or Gitelman Disease; Pregnant or nursing.

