1.3. Statistical Analysis: We will report means/medians and standard deviations (SD)/interquartile range (IQR) for all continuous measures, and frequency and proportions for categorical variables. Assuming a clinically significant difference between treatment groups of 3 ml/min/1.73m² and individual group SDs=3.5, a one-sided analysis t-test performed at $\alpha=0.05$ will achieve at least 80% power for a sample size of 42 if the participants will be allocated in a 2:1 ratio between treatment and control. We will also enroll participants into two cohorts to assure proportional distribution between non-glomerular (cohort A) and glomerular (cohort B) disease etiology. Our local pediatric CKD population composition by disease etiology is similar to national proportions of approximately 70% non-glomerular and 30% glomerular disease etiology. We will therefore over-sample the glomerular sub-population in cohort B and limit enrollment of the non-glomerular cohort A to n=19, maintaining roughly a 2:1 proportion. The goal allocation enrollment by treatment group and cohort size is summarized in **Table 2**. Two-sample t-tests on the GFR change score will be used to address Specific Aim 1A while separate 2-way ANOVA models with an interaction will be used to address Aim 1B. Repeated measures ANOVA models will be used to inform from all three time points in an intent-to-treat fashion.

Table 2: Goal allocation enrollment

Treatment Group	Allopurinol Group	Control Standard of Care Group
Cohort A: Non-glomerular disease etiology	19	7
Cohort B: Glomerular disease etiology	9	7
Total	28	14

Specific Aim 2. Determine the effect of Allopurinol treatment on Nlrp3 inflammasome and renal injury biomarkers.

2.1. Rationale and Objective: To our knowledge there are no studies that explore the effect of XO inhibition on the known mechanism of hyperuricemia induced Nlrp3 inflammasome activation and renal injury in a clinical trial setting. We therefore propose to establish whether XO inhibition reduces levels of these biomarkers at 3 and 6 months compared to baseline. If our hypothesis is correct that inflammasome-mediated renal injury is improved by Allopurinol, we expect to find that after 3 and 6 months of Allopurinol treatment, the biomarker levels will be reduced from baseline in both treated cohort groups compared to control participants.

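### The primary t-test on GFR change leaves out the etiology stratum, while Table 2 plans different cohort mixes in the two arms

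*Combined protocol and SAP*

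**What the plan says.** The Specific Aims and section 1.1 describe 2:1 allocation to Allopurinol or standard of care, stratified by etiology into cohort A (non-glomerular) and cohort B (glomerular).

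The primary outcome is worded in two ways:
- Specific Aims, Aim 1: the amount of GFR change over the 6 months "compared to the control group in both cohorts".
- Section 1.1: "The primary outcome of Aim 1A is change in GFR between baseline and 6 months by treatment group". The same paragraph continues: "An exploratory sub-aim (Aim 1B) will identify and compare GFR change by cohort characteristics". Disease etiology is one of the characteristics it lists.

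Section 1.3 says "Two-sample t-tests on the GFR change score will be used to address Specific Aim 1A" and reserves two-way ANOVA with interaction for Aim 1B. A further sentence mentions repeated measures ANOVA over the three time points. It names no cohort term and is not tied to Aim 1A.

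The only power statement is for the whole sample. "Assuming a clinically significant difference between treatment groups of 3 ml/min/1.73m²", "individual group SDs=3.5" and a one-sided 0.05 test, the design "will achieve at least 80% power for a sample size of 42" with 2:1 allocation.

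Table 2 sets the enrollment goals at 19 Allopurinol and 7 control in cohort A, and 9 and 7 in cohort B.

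**The concern.** A t-test on change compares the arms fairly when they are expected to be alike apart from treatment. Table 2 plans for them to differ in etiology, and Background and Significance lists glomerular etiology among the factors that speed progression. With more of the faster-declining patients in control, an unadjusted comparison credits part of the etiology difference to Allopurinol. More patients do not remove this, because the imbalance is planned and not due to chance.

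The stakes follow from the trial's purpose. The Specific Aims fault the earlier pediatric trial for not stratifying on known modifiers of GFR decline. They also say the GFR results here will feed directly into the effect size and sample size of a multicenter trial. A shifted estimate would be carried into that design.

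**Working it through.** **1. Reproduce the plan's figure.** Inputs from section 1.3: difference 3, SD 3.5, one-sided alpha 0.05, 28 versus 14.
- SE = 3.5 × √(1/28 + 1/14) = 1.146
- Noncentrality = 3/1.146 = 2.62, on 40 degrees of freedom
- Noncentral-t power = 82.4%

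This agrees with the stated figure of at least 80%. Among exact 2:1 splits, 42 is the smallest total that reaches 80% (26:13 gives 79.7%).

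**2. Compare Table 2 with the stated allocation.**

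| | Allopurinol | Control | Ratio |
|---|---|---|---|
| Cohort A | 19 | 7 | 2.7:1 |
| Cohort B | 9 | 7 | 1.3:1 |
| Total | 28 | 14 | 2:1 |

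The ratio is 2:1 only in the total. The glomerular share is 9/28 = 0.321 on Allopurinol and 7/14 = 0.500 on control, a gap of 0.179. The text of section 1.3 also limits cohort A to 19, whereas Table 2 gives 19 + 7 = 26.

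**3. Shift in the unadjusted difference.** Let δ be the mean GFR change in cohort A minus that in cohort B, apart from treatment. The expected unadjusted difference (Allopurinol minus control) is the treatment effect plus 0.179 × δ. Faster glomerular progression makes δ positive, so the shift favours Allopurinol. The documents give the direction but no size, so δ of 1 to 3 ml/min/1.73m² over six months is an assumption.

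**4. Effect on the type I error.** Trials were simulated at the Table 2 sizes with no treatment effect, normal changes with SD 3.5 in each arm-by-cohort cell, and the planned one-sided t-test.

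| Assumed δ | Shift (0.179 × δ) | One-sided type I error |
|---|---|---|
| 1 | 0.18 | about 6.6% |
| 2 | 0.36 | about 8.0% |
| 3 | 0.54 | about 9.3% |

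**5. If allocation is 2:1 within each cohort.** The glomerular shares are then equal and the shift is zero. The cohort spread stays in the error term, however. With one third glomerular it adds (1/3)(2/3)δ² to the variance of 3.5² = 12.25. At δ = 3 that is 12.25 + 2.0 = 14.25, an SD of 3.77. The t-test is unbiased but less precise than it need be.

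**6. Power with cohort in the model, at the Table 2 sizes.** The information from each cohort is n₁n₂/(n₁+n₂):
- Cohort A: 19 × 7/26 = 5.12
- Cohort B: 9 × 7/16 = 3.94
- SE = 3.5/√9.05 = 1.163, with 39 degrees of freedom
- Power = 81.3%

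This takes 3.5 as the within-cohort SD and counts no gain from baseline GFR.

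**7. Power if each cohort were tested separately.** With the same difference and SD assumed in each cohort, power is 59.4% in cohort A (19 versus 7) and 48.9% in cohort B (9 versus 7). The chance of significance in both is 0.594 × 0.489 = 29.1%.

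**The case against.** The strongest reply is that Table 2 may simply be wrong. The text specifies 2:1 with stratification by etiology, and the limit of 19 for cohort A also disagrees with the table. If the cells are a slip and each cohort is allocated 2:1, the bias disappears and an unadjusted t-test on change is a valid pilot analysis. This stands: the bias is conditional on Table 2 being followed. It does not remove the case for adjustment, which uses data already collected and helps precision whenever the cohorts differ.

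It may also be said that section 1.3 already plans a two-way ANOVA with interaction. That model is assigned to exploratory Aim 1B and does not change the Aim 1A test. Adding baseline GFR is good practice and corrects no separate error.

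A reader might infer a stronger point from Aim 1: that "compared to the control group in both cohorts" makes a separate test in each cohort primary, so the stated power is wrong. The documents do not support that. The phrase can equally mean across the two cohorts together. Section 1.1 defines the Aim 1A outcome by treatment group and makes etiology comparisons exploratory, and section 1.3 powers one overall 2:1 comparison. The plural in t-tests is thin evidence against this. Nor could a result in one cohort be presented as the primary finding without contradicting section 1.1.

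**Conclusion.** The primary analysis should include the stratum. Under Table 2 as printed, the unadjusted t-test is biased toward Allopurinol by 0.18 times the cohort difference in mean change. For an assumed difference of 1 to 3 ml/min/1.73m², the bias is 0.18 to 0.54, against a target difference of 3. The nominal 5% one-sided error rises to about 6.5% to 9.5%. The direction rests on the protocol's own statement about glomerular disease; the size rests on the assumed range. Under 2:1 allocation within cohorts the bias is nil and only precision is lost.

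The sample size calculation is not at fault: 42 gives the stated power for the overall comparison. The wording of Aim 1 is a clarification only. The cohort power figures of about 59% and 49% would matter only if separate cohort tests were meant as primary. They also assume a difference of 3 and an SD of 3.5 in each cohort, which the plan does not state; section 1.1 calls the expected change by etiology uncertain.

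**What to change.** 1. In section 1.3, name a single primary comparison: the overall treatment effect on GFR change from baseline to 6 months, from one model with treatment, cohort and baseline GFR. This costs one or two degrees of freedom and no new data. Power at N=42 is about 81% with cohort in the model, before any gain from baseline GFR.
2. Reconcile Table 2, and the limit of 19 for cohort A, with the stated 2:1 allocation stratified by etiology. If unequal ratios by cohort are intended, say so.
3. In Aim 1, say that the comparison is across both cohorts combined, to match section 1.1. Report cohort-specific effects with confidence intervals under exploratory Aim 1B.
4. If separate cohort tests were in fact meant as primary, the plan needs a power statement for each cohort and a multiplicity rule.

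Items 1 to 3 amount to a few sentences and a corrected table.

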Adult CKD clinical trials of Xanthine Oxidase (XO) inhibitors, which block the production of UA via the enzyme XO, have reduced UA and increased renal function, i.e. the glomerular filtration rate (GFR), over trial periods of 12 weeks to 2 years [19-21]. To date, only one 4-month pediatric CKD trial has been published by Sharbaf et al that showed treatment with Allopurinol, a XO inhibitor, improved GFR by a mean increase of $+16$ ml/min/1.73m², SD=9.3 compared to placebo [18]. The treatment also demonstrated a significant improvement in BP similar to another clinical trial of Allopurinol in a randomized 4-week crossover trial of hyperuricemia in pediatric essential hypertension [17]. The Sharbaf trial (2018) had study design flaws in that it did not use intention-to-treat principles, was not stratified for known modifiers of GFR decline, and did not report race. Additionally, none of the aforementioned clinical trials have explored the mechanism of how XO inhibitors improve GFR or BP, revealing an area for research. If benefits of GFR improvement from XO inhibition are reproduced in a well-designed pediatric CKD trial, this therapy could potentially offer hyperuricemic patients a significant improvement in disease burden. **We propose here a pilot clinical trial to identify the rate of GFR change following 6 months of Allopurinol treatment versus standard of care amongst pediatric hyperuricemic CKD patients. We hypothesize that Allopurinol therapy will reduce serum UA level and improve the rate of GFR change.** We will simultaneously explore a possible mechanism of Allopurinol therapy via reduced Nlrp3 inflammasome activity and expect to see a reduction of renal injury biomarkers. This study will address the feasibility of a design that stratifies the population for known modifiers of GFR decline with adequate power, essential preliminary data for designing a future large-scale multicenter pediatric trial.

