Uric acid (UA) is a purine nucleotide and fructose breakdown product via the enzyme Xanthine Oxidase (XO) which also generates harmful reactive oxygen species (ROS) byproducts. Two-thirds of serum UA is excreted by the kidneys through multiple regulation transporters, which can become inefficient in chronic kidney disease (CKD). Hyperuricemia develops by increased UA production, for example through a high purine meat or fructose diet, impaired renal UA excretion, or both. Large epidemiologic studies have recently associated hyperuricemia with incident acute and chronic kidney injury, a faster rate of renal function decline in both pediatric and adult chronic kidney disease (CKD), and an increased risk for death in CKD and dialysis patients [4, 8]. UA-mediated damage occurs along a “J” shaped pattern of injury, where it functions as a powerful anti-oxidant at mid-range levels and pro-oxidant at the extremes [10, 22]. Rat models of hyperuricemia show that mildly elevated UA causes crystal-independent renal injury through direct activation of the renin-angiotensin system, endothelial dysfunction through NADPH oxidase activation and ROS release [12]. In these animal models, induction of a mild hyperuricemia also results in pathologic changes to the renal functional nephron unit, i.e. glomerular hypertrophy and hyperfiltration, afferent arteriolar constriction, and tubular fibrosis which can be reversed with Allopurinol, a XO inhibitor [16].

Adolescents with UA levels above 5.5 mg/dL in the National Health and Nutrition Examination Survey (NHANES) 1999-2006 had a 2-fold increased odds of elevated blood pressure (BP)[9]. This value has since been used as a pediatric definition for hyperuricemia in several clinical studies and applied in this proposal [15, 17, 18]. A cross-over randomized controlled trial also demonstrated reduction of UA significantly improved systolic and diastolic BP in pediatric essential hypertension patients with hyperuricemia[17]. Clinical trials of XO inhibitors in adult CKD patients have demonstrated a reduced rate and in some, a reversal of decline in glomerular filtration rate (GFR) [21].

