2.2. Experimental Design: The study design of Aim 2 is the same as Aim 1 (see **Table 2**). We will measure the following biomarkers from reserved serum and urine samples at the baseline, 3, and 6 month visits. Activity of the Nlrp3 inflammasome will be measured via: serum high sensitivity CRP, Xanthine Oxidase

activity level, Nlrp3, Interleukins 1 β and 18, and urine Nlrp3 and IL-18. Renal injury biomarkers will be measured from serum NGAL, urine NGAL, NAG, KIM-1, and ET-1.

2.3. Statistical Analysis: We will report means/medians and standard deviations (SD)/interquartile range (IQR) for all continuous measures. Similar analyses will be used for Specific Aim 2 as Specific Aim 1. All sample size calculations were performed with nQuery Advisor v.7.0.

STUDY INTERVENTION ADMINISTRATION

The proposed intervention uses a study drug (Allopurinol) and concomitant therapy (Candesartan) that are available as generic. The PI is proposing to study the effects of Allopurinol under FDA-approved indications, which is approved for use in children and adults for the reduction of high uric acid levels. Candesartan is approved for use in children and adults for the reduction of high blood pressure. The concomitant therapy, Candesartan, is required in this protocol to reduce drug-drug interactions with Allopurinol. The medications Lisinopril, Enalapril, and Benazepril are commonly prescribed for hypertension but increase the risk of moderate to severe adverse reactions when used concomitantly with Allopurinol. Losartan is also a blood pressure lowering medication that uniquely lowers uric acid levels which could affect the results of the trial, but does not interact with Allopurinol so will be converted for a different and specific reason. Any participant in the trial who is prescribed Lisinopril, Enalapril, Benazepril, or Losartan at the time of randomization will be converted to a similar or same class of blood pressure lowering medication, Candesartan, which does not interact with Allopurinol or lower uric acid levels. Approximately 1/4 of participants in this trial will qualify for the Candesartan conversion. Candesartan will be supplied by the investigational pharmacy at no cost to participants. Allopurinol will also be supplied by the investigational pharmacy to the treatment group participants.

[figure not shown]
Recruitment and pre-trial medication adjustments:

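### Xanthine oxidase activity, which Allopurinol directly inhibits, is labelled in Aim 2 as a measure of Nlrp3 inflammasome activation and should be reported separately as target engagement

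*Combined protocol and SAP*

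**What the plan says.** The heading of Aim 2 in Specific Aims gives the objective: "Establish whether Allopurinol treatment reduces Nlrp3 inflammasome and renal injury biomarkers". The text below it sorts the markers into two groups and places XO activity in the first, the group for inflammasome activation: "hs-CRP, XO enzyme activity, Nlrp3", followed by IL-1 beta and IL-18. Section 2.2 (Experimental Design, Aim 2) does the same: "Activity of the Nlrp3 inflammasome will be measured via: serum high sensitivity CRP, Xanthine Oxidase" activity, then the remaining serum and urine markers. The classification is therefore deliberate and not a slip in the summary of aims.

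Elsewhere the protocol is clear about what XO is. Specific Aims describes XO inhibitors as drugs "which block the production of UA via the enzyme XO" and refers to "treatment with Allopurinol, a XO inhibitor". Background and Significance calls uric acid a "breakdown product via the enzyme Xanthine Oxidase (XO) which also generates harmful reactive oxygen species (ROS) byproducts". Specific Aims also says that mild hyperuricemia activates inflammatory mediators through the Nlrp3 inflammasome.

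Section 2.1 states the question for Aim 2: "We therefore propose to establish whether XO inhibition reduces levels of these biomarkers at 3 and 6 months compared to baseline". It expects the markers to be lower at 3 and 6 months in both treated cohorts relative to control. Section 2.3 says only that the analyses will resemble those of Aim 1. The documents name no key Aim 2 marker, set no rule for what result would support the hypothesis, and have no separate category for target engagement. Aim 2 is labelled exploratory.

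**The concern.** Section 2.1 asks whether inhibiting XO lowers a set of markers, and XO activity is a member of that set. To that extent the question is circular: it asks in part whether an XO inhibitor inhibits XO. In the protocol's own account, the chain runs from XO to uric acid to the inflammasome. A change in the first link shows that the drug acted. It does not show that the effect was carried to the last link.

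What is at stake is the mechanistic reading. The Impact paragraph hopes that the biomarker data may help to identify how XO inhibition works. If XO activity falls and is reported under the heading of inflammasome activation, the mechanism gains apparent support from a result that would be expected even if the mechanism were false.

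**Working it through.** **1. Count of measures (section 2.2).** Inflammasome: serum hs-CRP, XO activity, Nlrp3, IL-1 beta and IL-18 (5), plus urine Nlrp3 and IL-18 (2), giving 5 + 2 = 7. XO activity is 1 of these 7, or 1 of the 5 distinct markers named in Specific Aims. The other 7 − 1 = 6 measures are not the enzyme that the drug inhibits.

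**2. The plan's own figure (section 1.3).** Inputs: difference 3 ml/min/1.73m², SD 3.5 in each group, one-sided alpha 0.05, 2:1 allocation, N = 42. Table 2 gives totals of 28 and 14.

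- Standardised difference: 3 / 3.5 = 0.857.
- Standard error factor: √(1/14 + 1/28) = √0.1071 = 0.3273.
- Noncentrality: 0.857 / 0.3273 = 2.62, with 28 + 14 − 2 = 40 degrees of freedom.
- Power from the noncentral t distribution: 82.4%. The smallest 2:1 design with at least 80% power is 14 + 28 = 42.

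The stated sample size reproduces and is not in dispute. It confirms the test and group sizes used in the next step.

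**3. The same test applied to XO activity.** Section 2.3 carries the Aim 1 analyses over to Aim 2, so I use the same one-sided two-sample t-test on change from baseline with 28 and 14 participants. The documents give no expected fall in XO activity and no SD for it. The falls below are assumptions, in units of the SD of change. No effect on the inflammasome is assumed. Noncentrality is the assumed fall divided by 0.3273.

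| Assumed fall in XO activity | Noncentrality | P(significant), one-sided 0.05 | P(significant), two-sided 0.05 |
|---|---|---|---|
| 0.5 SD | 1.53 | 44% | 32% |
| 1.0 SD | 3.06 | 91% | 85% |
| 1.5 SD | 4.58 | 99.8% | 99.4% |

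The two-sided column is there because the one-sided choice is stated only for the Aim 1 sample size.

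**4. Comparison.** A measure that responded only to the inflammasome would be significant 5% of the time in the one-sided test if the drug had no effect on the inflammasome. XO activity would be significant 44% to 99.8% of the time over the assumed range. The excess over 5% is target engagement appearing under the inflammasome label.

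**The case against.** The strongest reply is that nothing in the plan lets XO activity settle Aim 2. The aim is exploratory, and there is no composite score and no rule that one positive marker suffices. The stated expectation is that the biomarkers in general will fall, so a fall in XO activity alone, with Nlrp3 and the interleukins flat, would not meet it on a literal reading. The markers are measured separately, six of the seven are not the direct target, and a reader can set XO aside. Change in serum uric acid is already a secondary outcome, and adherence is covered by pill counts and a visual analogue scale. All of this stands and limits the consequence. It does not correct the label: results reported as planned would still list XO activity as inflammasome activity.

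Several stronger conclusions are tempting but not supported:

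- A reader might infer that the drug's own action could by itself confirm Aim 2, or that the panel cannot tell target engagement from mechanism. The first needs a decision rule that the documents do not contain. The second overlooks the six other measures.
- A reader might infer that XO activity is almost certain to be significant. That holds only for assumed falls of about 1 SD or more. Section 1.2 reports that only 3 of 14 locally treated patients reached the uric acid target. The trial adds titration, but a large measured effect on the pathway still cannot be taken for granted.
- A reader might infer that XO activity has no bearing on the inflammasome. In the protocol's own chain it is an upstream component, so it is relevant to mapping the pathway. It is not a readout of inflammasome activation.
- A reader might also want hs-CRP moved out of the inflammasome group. The documents give no basis for that.

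**Conclusion.** The point holds as one of classification and interpretation. The protocol labels the activity of the drug's direct target as a measure of inflammasome activation, so a fall that is expected from target engagement would be counted towards the mechanism. The probability that XO activity alone is significant without any inflammasome effect is 44%, 91% or 99.8% for assumed falls of 0.5, 1.0 or 1.5 SD. These figures assume complete data on 28 and 14 participants, equal SDs, and the Aim 1 one-sided test at 0.05. The direction holds for any real fall in XO activity. The size depends on an effect that the documents do not give.

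The primary outcome, the sample size and the other six inflammasome measures are unaffected. The correction is still worth making, because it changes what a fall in XO activity may be taken to show about mechanism.

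**What to change.** In Aim 2 of Specific Aims and in section 2.2, take XO activity out of the list of inflammasome measures. Describe it as an upstream pharmacodynamic (target-engagement) marker, reported separately and alongside the change in serum uric acid. State that the conclusion about the inflammasome will rest on the remaining listed markers, chiefly Nlrp3, IL-1 beta and IL-18.

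The separation also makes a null result easier to read. If XO activity and uric acid fall but the inflammasome markers do not, the drug reached its target and the proposed mechanism is not supported. If XO activity does not fall, flat inflammasome markers say little about the mechanism.

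The cost is wording in two places. The same samples and assays are used, and no data are lost.

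### Pilot GFR differences, above all those within cohorts, are too imprecise to serve as effect sizes for the next trial; size it on a justified clinically important difference and take the SD and retention from the pilot

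*Combined protocol and SAP*

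**What the plan says.** The Impact paragraph that closes the Specific Aims gives the pilot's intended use: "GFR change from baseline to 6 months by treatment and cohort will be used to directly inform the effect size and sample size calculations" for a randomised multicentre paediatric trial. Elsewhere the Specific Aims describe the study as preliminary data for designing that trial.

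Section 1.3 sizes the pilot on a "clinically significant difference between treatment groups of 3 ml/min/1.73m²" with "individual group SDs=3.5", and states that "a one-sided analysis t-test performed at $\alpha=0.05$ will achieve at least 80% power for a sample size of 42", with participants "allocated in a 2:1 ratio between treatment and control". Table 2 gives 28 v 14 in total. The row "Cohort A: Non-glomerular disease etiology 19 7" is allopurinol then control, and the row for "Cohort B: Glomerular disease etiology" gives 9 and 7.

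Section 1.1 labels the comparison of GFR change by cohort characteristics (Aim 1B) exploratory. No section sets a precision target for the estimated difference, overall or by cohort. Nor does any section say that the next trial would use a confidence limit, a shrunken estimate or a fixed clinically important difference in place of the pilot's estimate.

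**The concern.** A pilot sized to detect a difference of 3 with about 80% power does not estimate that difference closely. Required sample size varies with the inverse square of the assumed effect, so moderate error in the estimate becomes large error in the next trial's size. The problem is sharpest by cohort, because each control cell holds 7 children and the sentence names cohort explicitly. An effect size read from those cells could give the next trial far too few children, or far too many, for reasons that have nothing to do with allopurinol.

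**Working it through.** **Inputs.** From section 1.3 and Table 2: difference 3, SD 3.5 in each arm, one-sided α 0.05, arm sizes 28:14, 19:7 and 9:7. The next trial's design is not in the documents. I assume a two-sided 5% test, 1:1 allocation, and a target power of 80% or 90%.

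**1. The plan's own figure.** SE = 3.5 × √(1/28 + 1/14) = 1.146. The noncentral t power at a difference of 3 is 82.4%, and 39 participants (26:13) would give 79.7%. So 42 is the smallest 2:1 total reaching 80%, and the stated power reproduces.

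**2. Precision of the estimates.** Half-width = t(0.975, df) × 3.5 × √(1/n₁ + 1/n₂).

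| Estimate | n | SE | t (df) | Half-width | 95% CI if 3 is observed |
|---|---|---|---|---|---|
| Overall | 28 v 14 | 1.15 | 2.021 (40) | 2.3 | 0.68 to 5.32 |
| Cohort A | 19 v 7 | 1.55 | 2.064 (24) | 3.2 | −0.19 to 6.19 |
| Cohort B | 9 v 7 | 1.76 | 2.145 (14) | 3.8 | −0.78 to 6.78 |

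The SE of the difference between cohorts in treatment effect is √(1.547² + 1.764²) = 2.35, with a half-width of about 4.75. If the SD were 9.3, the figure quoted in the Background for the one paediatric trial, the overall interval around 3 would be −3.15 to 9.15.

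**3. What this does to the next trial's size.** Per-arm n = 2 × [(1.960 + 0.842) × SD / d]², rounded up. For d = 3 and SD 3.5 the total is 44 (58 for 90% power, with 1.282 in place of 0.842). Putting in the unrounded limits of the overall interval gives totals of 822 at the lower limit and 14 at the upper. A trial of 14 has about 31% power by t-test at a true difference of 3.

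**4. Simulated consequence.** Pilots were simulated (60,000 per setting) with a true difference of 3 and SD 3.5. Each pilot's estimated difference and SD went into the formula in step 3, and the resulting trial's t-test power was computed at the true values. Every pilot with a positive estimate was kept.

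| Sized on | Power <60%, 80% target | Power <50%, 80% target | Power <50%, 90% target |
|---|---|---|---|
| Overall | 29% | 18% | 8% |
| Cohort A | 35% | 25% | 15% |
| Cohort B | 39% | 30% | 20% |

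At the 80% target, the 10th to 90th percentiles of the planned total run from 18 to 160 for the overall estimate and from 12 to 314 for cohort B. Error therefore runs in both directions.

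**5. Is the effect overstated?** With every positive pilot kept, the overall estimate averages 3.01 and the median next-trial total is about 42, close to the 44 from the true values. If only pilots significant at one-sided 0.05 lead to a next trial, the average estimate is 3.35 (3.35/3 = 1.12, so 12% too high) and 21% of next trials fall below 50% power at the 80% target.

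**6. Sensitivity to Table 2.** Section 1.3 limits cohort A to 19, whereas Table 2 shows 19 + 7 = 26; the two must be reconciled. If allocation were about 2:1 within cohorts (19:9 and 9:5), the SEs would be 1.42 and 1.95, and the conclusion would not change.

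**The case against.** Five points can be made on the other side.

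- **The wording is softer than a rule.** To inform a calculation is not to set it. The sentence excludes neither outside data nor a clinically important difference, and GFR change also yields the SD, which is a proper use of a pilot. This stands, and it limits the point to the absence of a safeguard.
- **A reader might infer that the plan, followed as written, gives the next trial an inflated effect and too few children.** The documents do not support that. They contain no rule that the next trial proceeds only after a significant pilot, and without one the overall estimate is essentially unbiased and the median size about right (step 5).
- **Target power matters.** At 90%, the chance of falling below 50% power drops to about 8% for the overall estimate. It remains 15% and 20% for the cohorts.
- **Powering on 3 is no cure.** Section 1.3 assumes 3 without justifying it, and it is the top of the adult range of roughly +1 to +3 in the Background. If the true difference is 2, a next trial sized on 3 with an upper limit for the SD has mean power of about 53%. Sizing on a significant pilot gives 52%, and sizing on any positive pilot gives 72%. This stands: the case for a fixed target is that it is stable and clinically argued, not that it guards against a smaller effect.
- **This trial's own analysis is untouched, and cohort comparisons are already exploratory.** Both are true. But the Impact paragraph gives those exploratory cohort results a confirmatory use in planning, and the label in section 1.1 does not undo that.

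**Conclusion.** The concern holds in a limited form. The stated use asks more of the cohort estimates than cells of 19 v 7 and 9 v 7 can give, because neither 95% interval would exclude zero at the planned difference. For the overall difference the problem is milder but still material: about 18% of next trials sized on it would fall below 50% power at an 80% target, and about 8% at a 90% target.

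These figures rest on SD 3.5, a true difference of 3, the arm sizes in Table 2, no dropout, and the assumed design of the next trial. A larger SD or losses to follow-up would widen every interval. Describing the overall estimate as mere noise would go too far, since its interval excludes zero when 3 is observed. Overstatement of about 12% arises only under the added assumption that a significant pilot is the condition for proceeding.

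**What to change.** Reword the Impact paragraph to say three things.

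1. The pilot will supply the SD of GFR change, used at an upper confidence limit, together with retention and adherence. With a one-sided 80% limit and 40 degrees of freedom the multiplier is √(40/χ²₀.₂₀,₄₀) = 1.112. An observed SD of 3.5 would be carried forward as 3.89, and the step 3 total for 80% power would rise from 44 to 54.
2. The next trial will be sized on a prespecified clinically important difference. Section 1.3 already states 3, but a justification should be added. The pilot's overall difference and 95% interval will be used only to judge whether that target is plausible.
3. Cohort differences will be reported with 95% intervals and not used as effect sizes.

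The cost is wording only, with no change to randomisation, endpoints, tests or enrolment in this trial. The drawbacks are that the next trial's planned size becomes less optimistic, and that its power is still not protected if the true difference is smaller than the chosen target.
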